The DSMB will have the authority to temporarily or permanently discontinue the trial if it perceives that harm is occurring due to the intervention. The DSMB will meet with the internal DSMC yearly to review adverse event reports, patient complaints if any, and enrollment rates. Data will be provided at these meetings by the investigators on key variables that may indicate harm (e.g., changes in self-report scores). The DSMB biostatistician will evaluate the confidentiality and integrity of the database and the procedures for recording and storing confidential files. The DSMB also will review the elements of the plan to manage emergencies.

Sample Size Determination for Proposed Analyses

For all study outcomes, Veterans will be randomly assigned (1:1) to the G-TBT and G-DST conditions. To reduce potential Type I errors, the primary outcomes of interest for Primary Aim 1 will be patient-reported IIRS, PCL, and DASS depression scores. The power analysis was calculated to be powered at 90% with a Bonferroni-corrected 1-tailed α = .0008 (.025/3 primary outcomes) to detect non-inferiority for G-TBT in comparison to the G-DSTs. Meta-analyses of group CBT for depression (McDermut, Miller, & Brown, 2001) and Group treatment for PTSD (Haagen et al., 2015; Sloan et al., 2013) found effect size estimates ranging from 0.56 (PTSD; Sloan et al., 2013) to 1.03 (depression; McDermut et al., 2001). In Veterans, Haagen et al. (2015) reported a Hedges g of 0.63. Thus, we conducted our power analysis with a conservative expected d of 0.60. Using procedures recommended by Chow, Shao, and Wang (2017) for non-inferiority designs, which utilize the pre-specified non-inferiority margin

(here prespecified as Δ d = 0) and the estimated effect in the active comparison treatment (d = 0.60), we determined that 152 participants (76 per cell) would be needed. However, this does not account for the group clustering effect.

Following Schnurr et al. (2001), we adjusted the sample size to account for potential group effects. Based on the intraclass coefficient (.025) found in the pilot G-TBT trial ([name] et al., 2018), an estimated 174 participants would be needed to adjust for potential clustering effects if groups average 8 participants. We adjusted the sample size upward 37% to adjust for potential discontinuation and 27% based on observed missing data for telehealth assessments, resulting in a final sample size of 326 participants (163 per cell).

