The full intent-to-treat (ITT) analysis set will comprise all randomized participants. Missing data in the full analysis set will occur if participants discontinue treatment prior to the end of the study or do not complete an outcome measure. Participants will not be discontinued from the study because of non-adherence and all will remain in the study unless consent is withdrawn or if there are concerns regarding participant safety. Missing data for the ITT analysis set will be imputed using multiple imputation (MI) methods, which are superior to most alternative missing data approaches even when data is missing completely at random (MCAR) or missing at random (MAR; Schafer & Graham, 2002; Enders, 2010). Although the use of MI will result in the least biased parameters, regardless of data missingness, several approaches will be undertaken to better understand the exact mechanisms for missing data. Little's (1988) MCAR test will be applied to all final models to determine whether data can be considered MCAR. Further, the results of analyses using study completers and protocol adherers (completer and per-protocol analyses) will be compared with results using the ITT analysis set to test sensitivity of study conclusions to study discontinuations and protocol non-adherence. Baseline differences also will be explored between treatment completers and those that discontinue. If baseline differences are detected, these covariates will then be included in the final model as auxiliary variables to improve the plausibility of assuming data is MAR (Collins et al., 2001; Enders, 2010; Graham, 2003;). Finally, discontinuation proportion will be used as one of the outcome measures of intervention feasibility.

Non-Inferiority Analyses (Primary Aim 1)

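### The plan says multiple imputation is least biased whatever the missingness, but it assumes data missing at random and no planned analysis tests departures from that

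*Combined protocol and SAP*

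**What the plan says.** The Missing Data section defines the ITT set as all randomized participants and states: "Missing data for the ITT analysis set will be imputed using multiple imputation (MI) methods". Stopping treatment is named as a source of missing data: "Missing data in the full analysis set will occur if participants discontinue treatment prior to the end of the study". The section has already rated MI above most alternatives under missing completely at random (MCAR) and MAR. It then goes further: "Although the use of MI will result in the least biased parameters, regardless of data missingness".

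Four checks follow:
- Little's test: "Little's (1988) MCAR test will be applied to all final models to determine whether data can be considered MCAR".
- Completer and per-protocol results, which "will be compared with results using the ITT analysis set to test sensitivity of study conclusions to study discontinuations and protocol non-adherence".
- A comparison of baseline values between completers and those who discontinue.
- Covariates that differ in that comparison, to be "included in the final model as auxiliary variables to improve the plausibility of assuming data is MAR".

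The sample-size section says: "We adjusted the sample size upward 37% to adjust for potential discontinuation and 27% based on observed missing data for telehealth assessments". The final size is 326. The Non-Inferiority Analyses section sets the margin at d = 0 and supports the claim when the confidence interval excludes 0.

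**The concern.** MI in its usual form fills in a missing outcome from observed patients who look alike on the variables in the model. If the unseen outcomes are systematically worse than that, the imputed values are too favourable. The plan describes no imputation model for data missing not at random (MNAR), and its own purpose for auxiliary variables is to make MAR more plausible. It therefore relies on MAR while claiming not to need it.

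Agreement between the ITT result and the completer or per-protocol result would not settle the matter. Those analyses leave out the patients in question and select on behaviour after randomization, so they rest on assumptions at least as strong as MAR.

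With a margin of 0, any bias toward G-TBT feeds straight into the non-inferiority decision.

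**Working it through.** **1. The plan's own sample size.**
- At d = 0.60, 90% power and one-sided alpha .025/3 = .00833, the usual two-mean formula gives 76 per arm, 152 in total, as stated. The printed alpha of .0008 would give 220.
- The design effect for groups of 8 at an intraclass coefficient of .025 is 1 + 7 × .025 = 1.175. Then 152 × 1.175 = 178.6, against the stated 174 (within 3%).
- From 174 to 326: 174 × 1.37 / 0.73 = 326.5, which matches. A 37% increase is the same as a 27% loss (1/0.73 = 1.37), so 174 / 0.73 / 0.73 gives 326.5 as well.

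**2. Loss allowed for.** The documents do not print a combined rate, so it has to be derived.
- From the totals: 1 − 174/326 = 46.6%.
- Both rates read as multipliers: 1 − 1/(1.37 × 1.27) = 42.5%.
- Both rates read as loss proportions: 1 − 0.63 × 0.73 = 54.0%.

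The last two readings do not reproduce 326 (they give 302.7 and 378.3), but they bound what the sentence could mean. I also use 27% missing as a low case, in which only the telehealth figure applies.

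**3. What each check can detect.**
- Little's test examines MCAR and cannot separate MAR from MNAR.
- Baseline comparisons and auxiliary variables use observed data. They can make MAR more credible but do not probe a departure from it.
- Completer and per-protocol analyses change who is analysed; they do not vary the unseen outcomes.
- The mixed model for Primary Aim 1 also relies on MAR.
- No section plans a delta adjustment, tipping point, reference-based imputation, pattern-mixture model or selection model.

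**4. Size of a departure (illustration).** Let m be the missing share, and let delta be how much worse than imputed the missing G-TBT outcomes are, in SD, beyond any such shortfall in G-DST.
- Bias toward G-TBT = m × delta.
- SE of d = sqrt(2 × 1.175 / 87) = .164, from 174 analysed participants, held fixed across the values of m.
- One-sided error rate at a true difference of 0 = 1 − Φ(z − m × delta / .164), with z = 2.394 at alpha .00833 and 3.156 at .0008.

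| Missing share | delta (SD) | Bias (SD) | Error rate, alpha .0083 | Error rate, alpha .0008 |
|---|---|---|---|---|
| any | 0 | 0 | 0.8% | 0.08% |
| 27% | 0.2 | .054 | 1.9% | 0.2% |
| 27% | 0.3 | .081 | 2.9% | 0.4% |
| 46.6% | 0.2 | .093 | 3.4% | 0.5% |
| 46.6% | 0.3 | .140 | 6.1% | 1.1% |
| 54% | 0.2 | .108 | 4.1% | 0.6% |
| 54% | 0.3 | .162 | 8.0% | 1.5% |

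**5. Tipping point (illustration).** Suppose the observed d is 0.60 in favour of G-TBT. At alpha .0083 the lower limit is 0.60 − 2.394 × .164 = 0.207. The claim is lost at delta = 0.207 / 0.466 = 0.44 SD with 46.6% missing (0.76 at 27%, 0.38 at 54%). At alpha .0008 the lower limit is 0.081, and the tipping values are 0.17, 0.30 and 0.15 SD in the same order.

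**The case against.** Several counter-arguments have force.

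- **The plan does more than compare analysis sets.** The feasibility section also compares discontinuation by arm, tabulates reasons for it and models attendance over time. A reader might infer that nothing planned would give any warning. That goes too far: unequal dropout and its reasons would be visible. None of these analyses, however, shows what the departure does to the non-inferiority result.
- **MAR is mentioned.** The section does speak of assuming MAR, so the fault in wording is one clause. The clause still contradicts that assumption.
- **The 47% is an allowance, not a forecast.** A reader might take it that nearly half the primary outcomes will be missing. The documents do not say so. Non-adherent participants stay in the study and may still be assessed. The 27% comes from telehealth assessments, and in-person ones are allowed. There is a mid-treatment battery, and the PCL-5 is also given every other session, so many who drop out may have later data to inform imputation. This is why the low case of 27% is shown.
- **The bias needs asymmetry.** A reader might infer that worse outcomes among the missing always favour G-TBT. They do so only when the shortfall, weighted by loss, is larger in G-TBT. The documents give no evidence that it will be. Asymmetry is possible because the therapies differ, and observed data cannot rule it out.
- **Meaning of the error rate.** At a true difference of exactly 0 the two therapies are equal, so the rate describes the boundary of the null hypothesis, not acceptance of a plainly inferior treatment.
- **Alpha.** The printed .0008 and .025/3 disagree. That is a separate matter, but the error rates depend on it, so both are given.

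These points limit the size of the concern. They do not supply the missing analysis.

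**Conclusion.** The concern holds in this limited form: one statement about MI is wrong, and the non-inferiority conclusion has no planned test against departures from MAR. The documents do not show that the result will be biased, or in which direction.

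If the departure is worse in G-TBT by 0.2 to 0.3 SD and 27% to 54% of outcomes are missing, the boundary error rate becomes 1.9% to 8.0% instead of 0.8% at alpha .0083, or 0.2% to 1.5% instead of 0.08% at .0008. These figures rest on an assumed delta, an SE taken from the planned 174 analysed participants, and similar loss in both arms. The sponsor should make the change, since a substantial share of outcomes may be imputed and the margin leaves no slack.

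**What to change.** In the Missing Data section, delete the words claiming that the result holds whatever the missingness, and state that the planned MI assumes MAR.

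For IIRS, PCL-5 and DASS depression, add a pre-specified delta-adjusted MI. It should worsen the imputed G-TBT scores only, in steps of 0.1 SD from 0 to 0.5 SD. Report the value at which the claim is lost, or that it is not lost within the range, beside each non-inferiority conclusion. Write this down before outcomes are compared by arm.

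Keep the completer and per-protocol analyses as supportive, but no longer present them as the test of robustness to missing data.

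The cost is a wording change and a few extra runs on data sets that will already have been imputed, with no new patients or visits. The downside is that a claim may have to be reported as sensitive to missing data.

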All assessment and treatment providers will be trained and supervised by the Principal Investigator, who is a licensed psychologist (and with backup supervision coverage from [name], licensed psychologist). At intake, participants identified by clinical interview with suicidal ideation and acute intent will be excluded from the study and immediately offered emergency psychiatric care at the VAMC. During the duration of the study, the Principal Investigator (or covering Co-Investigator) will immediately contact the participant and assess suicide risk when any instance of suicide risk is identified (preferably before the participant leaves the appointment). If suicidal ideation is present but not intent, the participant will be retained in the study and reassessed for suicide risk by the investigators in one week. In cases of acute suicidal intent, state law requires immediate hospitalization and these guidelines will be followed.

Assessment of Quality of Life, Psychological Well-Being, Social Reintegration, Psychiatric Symptomatology, and Treatment Satisfaction

The battery of self-report questionnaires and a diagnostic interview will be completed pre-, mid-, and post-treatment and at the 6-month follow-up to track participants' progression through treatment and maintenance. The mid-treatment assessment will include the self-report questionnaires only (no diagnostic interview). Following the initial assessment at pre-treatment, all assessment sessions will be completed either in-person and via VA-approved telehealth technologies, based upon the preference of the participant. These time points for the assessments are consistent with CBT research with Veterans with depressive/anxiety disorders, as well as with the Pl's CDA. Participants will be compensated \$40 for pre-treatment, \$60 for mid-treatment, \$80 for post-treatment, and \$120 for 6-month follow-up for completion of assessment procedures for a total of \$300 for the entire study. To reduce the likelihood of missing data, all assessments will be scheduled separately from normal treatment sessions. Assessments of quality of life, social reintegration, and general symptoms of the depressive/anxiety disorders, rather than multiple disorder-specific questionnaires, were chosen due to the

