The continuous measures of quality of life, psychological well-being, and social reintegration are CHART (disability), CRIS and CHART (social reintegration), IIRS and V/SF-36 (quality of life and impairment), APPQ (agoraphobia, social anxiety, and interoceptive avoidance), DASS (depression, anxiety, and stress), ADIS-5 (disorder dimensional severity scales), PCL-5 (PTSD), and STICSA-Trait (cognitive and somatic anxiety). Although multiple variables will be examined, the primary outcomes of interest will be IIRS, PCL-5, and DASS depression scores. All other analyses will be conducted in an exploratory fashion to inform future studies. Parameter estimates to calculate the effect size difference will be arrived at using three-level (measurement occasions nested within participants nested within assigned treatment group) generalized mixed-effects regression models (MRM). MRM is a method of repeated measures analyses that allows for modeling of continuous and categorical independent and dependent variables and for appropriate modeling of covariance structures when observations are correlated across time and/or across group. This analytic approach fully captures variability in outcomes across multiple follow-up assessments and accounts for any potential effect of the group to which a participant is assigned and is thus preferred over methods that collapse data over time. We will calculate between-group treatment differences as the d, based on the effect of treatment condition on the intercept parameter when the model is centered on post-intervention and on the effect of treatment condition on the intercept parameter when the model is centered on month 6. We prespecified the non-inferiority margin (d) to be 0 (indicating we expected G-TBT to be at least equivalent to G-DST) and the one-sided CI for our three primary analyses at $\alpha = .0008$. In the primary analyses of outcome variables, we will covary for the baseline value of the variable of interest. We will also include the linear effect of time as well as a time by condition interaction effect to determine whether treatment differences (or lack thereof) were stable from post-intervention through the follow-up. Additional covariates (e.g. age, number of psychiatric comorbidities, race, sex, combat theatre, and number of treatment sessions) will be added to the model to adjust for putative confounding variables. Effect size CIs that do not contain 0 provide evidence in support of noninferiority for G-TBT.

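### The one-sided alpha is printed as .0008, but .025/3 is .0083 and only .0083 reproduces 76 per cell; separately, no rule says which of two time points decides each primary outcome.

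*Combined protocol and SAP*

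**What the plan says.** **Alpha.** The section Sample Size Determination for Proposed Analyses sets 90% power at a "Bonferroni-corrected 1-tailed α = .0008 (.025/3 primary outcomes"). It takes a margin of zero and "the estimated effect in the active comparison treatment (d = 0.60"), and concludes: "we determined that 152 participants (76 per cell) would be needed". Later adjustments for clustering, discontinuation and missing telehealth assessments bring the total to 326. The section Non-Inferiority Analyses (Primary Aim 1) repeats .0008 as the operative level, setting "the one-sided CI for our three primary analyses at" that value.

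**Time points.** The same analysis section names IIRS, PCL-5 and DASS depression as primary. It takes the between-arm d from the treatment effect on the intercept with the model "centered on post-intervention and on the effect of treatment condition on the intercept parameter when the model is centered on month 6". One success sentence follows: "Effect size CIs that do not contain 0 provide evidence in support of noninferiority for G-TBT". A time-by-condition term is included to show whether differences stay stable through follow-up. The assessment section says only that the battery "will be completed pre-, mid-, and post-treatment and at the 6-month follow-up"; it ranks none of these visits.

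**The concern.** The printed alpha and its printed derivation differ by a factor of about ten. Because .0008 reappears as the level of the confidence interval, an analyst who follows the analysis section literally would build intervals that the trial was not sized for. A result could then fail at .0008 that would have passed at the level behind the sample size.

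The time-point gap is separate. Three outcomes at two times give six intervals, and the correction divides by three. If an outcome passes at one time and fails at the other, the plan does not say whether that counts as success, so the choice could be made after the results are seen.

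**Working it through.** **Inputs.** From the sample-size section: one-sided alpha .0008, derived as .025/3; power 90%; d = 0.60 (SD = 1); margin 0; 76 per cell before clustering. Allocation is 1:1. From the analysis section: three primary outcomes, two time points, success if the interval excludes 0. The documents give no correlations between outcomes or times, so those below are assumptions shown as ranges.

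**1. Division.** .025/3 = .00833, and .00833/.0008 = 10.4.

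**2. The plan's sample size.** The plan cites a textbook procedure but prints no formula. The standard normal approximation is n per cell = 2 × [(z(1−α) + z(.90)) / 0.60]², with z(.90) = 1.2816.

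| One-sided α | z(1−α) | n per cell | Rounded up |
|---|---|---|---|
| .00833 | 2.394 | 75.05 | 76, as stated |
| .0008 | 3.156 | 109.4 | 110 |

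Of the two values in the document, only .0083 reproduces 76. Any one-sided value from about .0078 to .0084 also rounds up to 76, so the match supports .025/3 without proving it to the last digit. A noncentral-t version gives 77 and 112.

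**3. Power at 76 per cell.** Φ(0.60 × √38 − z(1−α)), with 0.60 × √38 = 3.699:
- at .00833: Φ(3.699 − 2.394) = 90.4%
- at .0008: Φ(3.699 − 3.156) = 70.6%

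The size ratio does not depend on d: (3.156 + 1.2816)² / (2.394 + 1.2816)² = 1.46.

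**4. Observed d needed at 76 per cell (illustrative).** z(1−α)/√38 is 2.394/6.164 = 0.39 at .00833 and 3.156/6.164 = 0.51 at .0008. An observed d between these passes at one level and fails at the other. This is an unadjusted two-sample z-test without clustering. The planned model adjusts for baseline; with an assumed baseline correlation of .5, both figures shrink by √(1 − .25) = 0.866, to about 0.34 and 0.44.

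**5. Family-wise error over the two time points, arms exactly equal.** The Bonferroni bound for six tests at .00833 is 6 × .00833 = .050. Multivariate-normal integration over three outcomes and two times gives:

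| Assumed correlation, outcomes / times | Either time counts | One named time |
|---|---|---|
| .3 / .4 | .045 | .024 |
| .5 / .6 | .040 | .022 |
| .7 / .8 | .031 | .020 |
| .8 / .9 | .025 (.0254) | .018 |

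If both times are required, the error is .010 or less over this range. At .0008, six tests spend at most 6 × .0008 = .0048.

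**6. Power if both times are required.** At 76 per cell, α = .00833 and d = 0.60 at both times, per-outcome power falls from 90.4% to 81.7% (time correlation 0) and 87.4% (correlation .9).

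**7. How often the two times would disagree (illustrative).** On the simplified test of step 4 at .00833, with the same true difference at both times and a time correlation of .4 to .8, one outcome splits in 1.5% to 1.1% of trials at a true difference of 0, and in 31% to 18% at 0.3.

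**The case against.** The best defence on alpha is that .0008 is a decimal slip. The derivation stands beside it, the sample size confirms the derivation, and the intended value can be recovered. That is the most plausible explanation, and it stands. It does not remove the need for correction, because the analysis section carries .0008 alone, with no derivation, as the level to be applied.

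On time points, the reference to three primary analyses suggests one test per outcome, and the time-by-condition term is a prespecified tool for reading differing results. Both observations are fair. But the plan does not say which of the two intervals is the test, and the interaction describes stability without assigning alpha or deciding a split result.

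A reader might infer that the plan inflates Type I error. The documents do not support this. Exceeding .025 needs two things together: .0083 as the level, and success at either time being enough. The plan prints .0008 and states no either-counts rule. Even then the excess is small when correlations are high (.0254 at .8/.9).

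A reader might also infer that the trial has only 70.6% power. That figure belongs to the 76-per-cell basis with .0008 applied literally, not to the 163 per cell to be randomized, which includes allowances for clustering, discontinuation and missing data. It also takes 0.60 at face value, although the plan defines 0.60 as the comparator's effect and describes its margin as "indicating we expected G-TBT to be at least equivalent to G-DST".

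**Conclusion.** The alpha is wrong as written. It is a factor of 10.4 below its own derivation, and the stated 76 per cell agrees with the derivation and not with the printed value. Applied literally, .0008 would call for 110 per cell instead of 76, 1.46 times as many for the same power whatever the true difference. The 110 and the 70.6% rest on the normal approximation and on d = 0.60; neither 0.60 as a between-arm difference nor 90% as the trial's power is endorsed here.

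The time-point gap is real but secondary and conditional. It becomes an error-rate problem only once alpha is corrected to .0083 and either time is allowed to count: about .045 to .025 at the assumed correlations, never above .050. Under any reading, the handling of a split result is left open. The cut-offs of 0.39 and 0.51 and the split rates only illustrate scale.

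**What to change.** **1. Alpha.** Replace .0008 with .0083 (.025/3) in both the sample-size section and the non-inferiority analysis section. If .0008 is intended, restate its derivation, the power and the sample size. Correcting to .0083 leaves the plan's own size calculation unchanged.

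**2. Time points.** In the non-inferiority analysis section, adopt one of two rules:
- name one primary time point for all three outcomes at one-sided .0083 and, for each outcome, test the other at .0083 only after the first succeeds; or
- require both time points to succeed at .0083.

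Either rule holds .0083 per outcome and .025 overall. The sponsor chooses the rule and any order, and adds one sentence on how a split result is reported.

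**Timing.** Settle this before any outcome data are analysed by arm. Unblinding is not a usable deadline, since under Randomization Procedures the analyst in charge of randomization already knows the assignments.

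**Cost.** The change is to wording only. Under the first rule the second time point loses independent confirmatory status. Under the second, per-outcome power at 76 per cell falls from about 90% to about 82% to 87%, assuming d = 0.60 at both times.

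### A non-inferiority margin of d = 0 makes the primary test a superiority test, and its stated 90% power requires G-TBT to beat G-DST by 0.60

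*Combined protocol and SAP*

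**What the plan says.** The Objective describes a non-inferiority comparison of G-TBT with G-DST. Two later sections of the combined protocol and SAP fix the margin at zero.

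- **Sample Size Determination for Proposed Analyses.** The margin is "here prespecified as Δ d = 0". The other input and the result are "the estimated effect in the active comparison treatment (d = 0.60), we determined that 152 participants (76 per cell) would be needed". The 0.60 is drawn from meta-analyses of group treatment for depression and PTSD. On power, the text reads "The power analysis was calculated to be powered at 90"%, for detecting non-inferiority, at a one-tailed alpha printed as .0008 and explained as .025/3.
- **Non-Inferiority Analyses (Primary Aim 1).** "We prespecified the non-inferiority margin (d) to be 0 (indicating we expected G-TBT to be at least equivalent to G-DST"). The decision rule is "Effect size CIs that do not contain 0 provide evidence in support of noninferiority for G-TBT".

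The analysis section also bears on how the test behaves. The between-arm d is estimated at post-intervention and again from "the effect of treatment condition on the intercept parameter when the model is centered on month 6", and neither is named as decisive. For the primary outcomes, "we will covary for the baseline value of the variable of interest". Further covariates such as age, race, sex "and number of treatment sessions) will be added to the model to adjust for putative confounding variables".

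**The concern.** A non-inferiority test asks whether the new treatment is worse than the comparator by more than a tolerated amount. With a tolerated amount of zero, the null hypothesis becomes that G-TBT is no better than G-DST, and rejecting it shows superiority. The label and the test then disagree.

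The power statement is affected more seriously. The usual reason for a non-inferiority design is that the two treatments may be about equally good. In that case a zero-margin test has no power beyond its alpha. A streamlined therapy that works as well as the disorder-specific ones would almost certainly end with an interval that includes 0 and be read as not shown to be non-inferior. The interval would still show how much inferiority is excluded, but there would be no prespecified non-zero margin to judge it against.

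**Working it through.** **Inputs.** From the sample-size section: d = 0.60 (SD units), margin 0, 90% power, one-sided alpha .025/3 = .00833 (printed .0008), 1:1 allocation, ICC .025, groups averaging 8, and totals of 152, 174 and 326. Normal quantiles: z(.025/3) = 2.394, z(.0008) = 3.156, z(.90) = 1.282.

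**1. Reproducing the plan's figure.** With D the distance from the true difference to the margin, n per arm = 2(z_a + z_b)² / D².

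- At .025/3: 2(2.394 + 1.282)² / 0.60² = 75.05, so 76 per cell and 152 in total. This matches.
- At .0008: 2(3.156 + 1.282)² / 0.60² = 109.4, so 110 per cell. This does not match.

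The calculation therefore used .025/3 and D = 0.60.

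**2. What D = 0.60 means.** D = (true G-TBT advantage) + (margin). With margin 0, the true advantage must be 0.60. That is as large as the whole effect assumed for the comparator.

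**3. Power at other true differences.** Design effect = 1 + (8 − 1) × .025 = 1.175. I take 174 analysed (the plan's target after clustering) and 326 analysed (an optimistic ceiling, since 326 already allows for 37% discontinuation and 27% missing assessments). Effective n per arm is 174/1.175/2 = 74.0 and 326/1.175/2 = 138.7. Unadjusted power = Φ(d√(n_eff/2) − z_a), with success on the side favouring G-TBT.

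| True advantage d | .025/3: 174 | .025/3: 326 | .0008: 174 | .0008: 326 |
|---|---|---|---|---|
| 0 | 0.83% | 0.83% | 0.08% | 0.08% |
| 0.2 | 12.0% | 23.3% | 2.6% | 6.8% |
| 0.3 | 28.5% | 54.2% | 9.2% | 25.6% |
| 0.6 | 89.6% | 99.5% | 69.0% | 96.7% |
| Smallest observed d that succeeds, z_a√(2/n_eff) | 0.393 | 0.287 | 0.519 | 0.379 |
| d for 90% power, (z_a + z_b)√(2/n_eff) | 0.604 | 0.441 | 0.729 | 0.533 |

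Because power depends only on D, the last row is also the margin that would give 90% power at true equality.

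**4. Several tests at equality.** By the Bonferroni bound, the chance of any success over three outcomes is at most 3 × .00833 = 2.5% at one time point (0.24% at .0008). If either time point may count, it is at most 6 × .00833 = 5% (0.48%).

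**5. Baseline adjustment.** The documents give no baseline–outcome correlation. Assuming r = 0.5 to 0.7 and a variance factor of 1 − r², power at d = 0.3 becomes 39–56% (174) and 69–87% (326) at .025/3, or 15–27% and 39–63% at .0008. At d = 0 it stays at alpha. With number of treatment sessions, a post-randomisation variable, in the model, the rate at equality need not be exactly alpha.

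**The case against.** The strongest defence is that a zero margin is openly stated twice and is only strict: it cannot let an inferior treatment through, and the expectation given for it includes superiority. That stands as far as it goes. The zero margin does not raise the rate of false non-inferiority claims; the 5% bound above comes from counting two time points, a separate matter. But strictness does not rescue a 90% power statement that needs an advantage of 0.60.

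The authors may have meant a margin of 0.60 with a true difference of 0, which gives the same 76 per cell. That reading contradicts both statements of the margin, and it would allow G-TBT to lose the comparator's entire assumed effect.

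The plan never says that an interval including 0 means failure, nor which direction of d favours G-TBT. Both are inferred here from the ordinary meaning of a margin. The public document also has no background section and cites the G-TBT pilot without reporting its effects, so an expected advantage could be written elsewhere; none appears here.

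On the arithmetic, 174 is not a floor. If the two losses are independent, 326 × .63 × .73 ≈ 150 are analysed, n_eff = 150/1.175/2 = 63.8, and power at 0.60 is Φ(0.60√31.9 − 2.394) = 84%. In the other direction, the plan's own step from 152 to 174 is a factor of 1.145, slightly below 1.175. Neither changes the result at equality.

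**Conclusion.** The concern holds. As written, the primary test is a one-sided superiority test under a non-inferiority label. Its 90% power, as calculated, applies to a true G-TBT advantage of 0.60 at one-sided .025/3, and nothing in the documents predicts an advantage of that size. At true equality each test succeeds with probability 0.83% (0.08% at the printed .0008) at any sample size. Even with all 326 analysed, unadjusted power at .025/3 is 23% for an advantage of 0.2 and 54% for 0.3.

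The result at equality assumes a valid test of one outcome at one time point, favouring G-TBT, without adjustment for post-randomisation variables. The other power figures also assume the plan's ICC and group size, and no gain from baseline adjustment except where r is stated.

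**What to change.** **Minimum.** Relabel the primary test as superiority, and state that the 90% power, as calculated, refers to a true G-TBT advantage of 0.60 at one-sided .025/3. This is a text amendment with no added enrolment or data collection. The price is a less favourable power statement and the loss of the non-inferiority label.

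**Alternative, only if no outcome data have been seen by arm.**

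1. Reconcile .0008 with .025/3.
2. Name the deciding time point, and leave number of treatment sessions out of the deciding model.
3. Prespecify a non-zero margin for each primary outcome, justified clinically and against the comparator's effect.
4. Conclude non-inferiority when the one-sided bound clears the margin, and test superiority only afterwards.
5. Keep 326 and restate power at a true difference of 0.

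With all 326 analysed and no adjustment, 90% power at equality needs a margin of about 0.44 at .025/3, or 0.53 at .0008. For a margin of 0.30, assumed purely for illustration, power at equality is 28–54% at .025/3 (9–26% at .0008). Reaching 90% would take 2(2.394 + 1.282)²/0.30² × 1.175 = 300.2 × 1.175 ≈ 353 analysed per arm, or 437.6 × 1.175 ≈ 514 at .0008.

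This route also costs credibility. Moving the margin away from 0 loosens the success criterion in a document dated June 2022, so it needs a dated, documented, blinded amendment. Whether that is still possible cannot be verified. Under Data Monitoring Board, investigators supply self-report score changes at yearly meetings, without saying whether by arm. The PCL-5, a primary outcome, is also given every other treatment session in groups that are arm-specific. If scores have been seen by arm, only relabelling remains.
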